## **6.2 Description of Assessments**

Safety and efficacy evaluations will be performed during the study. The schedule of these procedures is described in [Table 6.1.1](#).

### **6.2.1 Baseline Characteristics**

#### **6.2.1.1 Demography**

Information relating to the subject's gender, age, race, and weight/height will be collected at screening and recorded on the appropriate eCRF page.

#### **6.2.2 Medical History**

The medical history of each subject will be collected and recorded on the appropriate eCRF page. This history will also include any abnormalities found during the physical examination conducted at the Screening Visit. History of prior and concomitant medications will be recorded as indicated in Section [5.9](#).

#### **6.2.3 Efficacy Parameters**

As much as possible, the same individual should perform a given efficacy assessment at every visit when the assessment is required. Efficacy will be assessed by the following measures collected during the study:

##### **6.2.3.1 Primary Efficacy Variable**

The primary efficacy endpoint is the change in AISRS total score from Visit 2 (Baseline) to Visit 7 (End of Study) in AR19 treated subjects compared to placebo.

### **6.2.3.2 Secondary Efficacy Variables**

- CGI-S at Visit 7 compared to Baseline
- CGI-I at Visit 7
- Changes from Baseline of AISRS subscale scores compared to Visit 7
- Changes from Baseline of the BRIEF-A, subscales, indices, and composites compared to Visit 7

### **6.2.3.3 Exploratory Endpoints**

Items pertaining to emotional dysregulation are contained in certain domains of several existing tools, including the BRIEF-A, DERS, and ASQ, which will be used in this study.

Exposure-response relationships using population pharmacokinetics will be explored. A nonlinear mixed-effect modeling approach will be used for population pharmacokinetic analysis. To aid the population pharmacokinetic analysis, two blood plasma samples will be collected from all subjects. **Error! Reference source not found.** provides instructions on processing and shipment of samples to the central laboratory. The samples collected will include pre-dose up to approximately 6 hours following drug administration on planned subject visit days (Visit 6 and Visit 7). Subjects should be instructed to record accurate dosing history (date/time) on their dosing card for the day prior to and day of their study visit. Additional AR19 concentration vs time data may be pooled from other studies and included in population pharmacokinetic analysis. Covariates such as age, weight, liver function (AST and ALT), CYP 2D6 metabolizer status, and race and their effect on AR19 pharmacokinetic parameters will be explored. The developed population pharmacokinetic model will be used to conduct exposure-response analysis.

## **6.3 Assessments**

### **6.3.1 Adult ADHD Investigator Rating Scale (AISRS)**

The AISRS is a validated 18-item scale that corresponds directly to the 18 ADHD items in the Diagnostic and Statistical Manual of Mental Disorders. It includes adult prompts for each item. The AISRS will be used to determine trial eligibility. An AISRS assessment will be completed at Study Visits 1 through 7. The Investigator or other designated, qualified individual from the study research team will complete the assessment.

### **6.3.2 Clinical Global Impression Scales (CGI)**

The Clinical Global Impression Scales are used to measure features associated with ADHD. A global assessment of disease severity (CGI-S) will be completed at Study Visits 1 through 7. A global assessment of disease improvement (CGI-I) relative to baseline will be completed at Study Visits 3 through 7. The Investigator or designated, qualified individual from the study site will perform the assessment.

### **6.3.3 Mini International Neuropsychiatric Interview 7.0.2 (MINI)**

The MINI is a short, structured diagnostic interview developed for DSM-5™. It assesses the 15 most common psychiatric diagnoses and can be completed in about 15 minutes. The MINI will be completed at Screening.

### **6.3.4 Conners' Adult ADHD Diagnostic Interview for DSM-IV™ (CAADID)**

The CAADID is a structured interview that assesses childhood and adult ADHD symptoms. Although the version used was designed for DSM-IV™, it can be adapted to make an ADHD diagnosis using DSM-5™ criteria.

### **6.3.5 Behavior Rating Inventory of Executive Function–Adult Version (BRIEF-A)**

The BRIEF-A is a standardized measure designed to assess adult executive functioning and self-regulation. It is composed of 75 items and 9 clinical scales which include: Inhibit, Self-Monitor, Plan/Organize, Shift, Initiate, Task Monitor, Emotional Control, Working Memory, and Organization of Materials. The clinical scales compose two indexes: Behavioral Regulation (BRI) and Metacognition (MI), and these indexes form the overall summary score, the Global Executive Composite (GEC).

### **6.3.6 Difficulties in Emotional Regulation Scale (DERS)**

The DERS is a validated non-disease state scale consisting of 39 items. These items are grouped to reflect difficulties in: a) awareness and understanding of emotions; b) acceptance of emotions; c) ability to engage in goal directed behavior and refrain from impulsive behavior while experiencing negative emotions; and d) access to emotional regulation strategies perceived as effective.

### **6.3.7 Affective Style Questionnaire (ASQ)**

The ASQ is a 20-item questionnaire used to measure individual styles in emotional regulation. The styles assessed in this instrument are: a) suppression and other strategies to conceal or avoid emotion; b) more able to access emotional information in adaptive problem solving (i.e., to be better able to modulate emotional experience and expression according to contextual demands); and c) reflecting comfort and non-defensiveness in response to arousing emotional responses, thus tolerating the aroused emotional response.

## **6.4 Safety Parameters/Assessments**

All subjects who enter the study will be assessed for safety. Safety will be monitored by AEs assessed at each post-dose visit. In addition, the C-SSRS will be administered at Screening and all subsequent scheduled visits to assess emergent suicidal thoughts or behaviors. Medical history will capture all medical conditions at Visits 1 (Screening) and 2 (Baseline). Physical examinations and clinical laboratory tests will be conducted at Visit 1 (Screening) and Visit 7 (End of Study), and at an Early Termination Visit, if necessary and can be conducted at any post-dose visit, if the Principal Investigator deems it necessary.

The following will be assessed throughout the study according to the Schedule of Events [Table 6.1.1](#):

- Incidence and severity of AEs (see Section 7).
- Incidence of clinically significant changes from Baseline in the C-SSRS.

#### **6.4.1 Physical Examination**

A full physical examination will be performed at Visits 1 (Screening), 7 (End of Study), and at an Early Termination Visit, if necessary. This will include physical examination of the following body areas and systems: head and neck, abdominal, chest, cardiovascular, heart, respiratory, musculoskeletal, skin, neurological, and endocrine. This assessment is optional at unscheduled visits, per the Investigator's discretion.

Body weight will also be measured at Screening (Visit 1), Baseline (Visit 2), and at the End of Study (Visit 7) or at the Early Termination Visit, if necessary.

#### **6.4.2 Vital Signs**

Blood pressure and pulse will be assessed at all study visits and will be taken using automated machines programmed to take 3 consecutive readings (at least 2 minutes apart). Subjects should be comfortably seated for at least a few minutes prior to blood pressure readings. Respiratory rate, height for BMI, and temperature will be measured at Screening (Visit 1) only.

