### **1.1.3 Rationale for Development of AR19 in ADHD Adults**

Racemic amphetamine was the first stimulant studied for treatment of behavioral disorders in children in 1937. However, only one study has been conducted to date documenting the efficacy of a 50% d-amphetamine and 50% l-amphetamine compound (Evekeo®) in the treatment of ADHD.

This study was conducted in children ages 6 to 12 years and demonstrated efficacy beginning at 45 minutes and continuing through 10 hours after administration of a single dose. No studies evaluating the effects of this mixture of d:l amphetamine have been completed in adults. The current study will test the safety and efficacy of this composition (AR19) in adult subjects 18 through 55 years old with ADHD.

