#### **6.1.3 Treatment Period – Day 2 to Day 36 (±2)**

Enrolled subjects will begin taking study medication at home the morning following the Baseline Visit at 10 mg/day or placebo. From Day 2 through Day 36 (±2) inclusive, subjects will swallow study medication (2 capsules) once daily in the morning with or without food, and again four to six hours later. The dosing regimen will be twice daily for the duration of the study (4 capsules/day).

The following activities will be performed at each visit:

- Blood pressure and pulse (in triplicate via automated machine)
- AISRS
- CGI-S
- CGI-I
- Follow-up C-SSRS
- Adverse events assessment
- Concomitant medications assessment
- Pharmacokinetic sampling\* (Visit 6 only)
- Urine pregnancy test for females of child-bearing potential (Visits 4 and 6 only)
- eCRF entry for study drug assignment
- Study drug accountability and study medication training
- Dispense study drug

\*Blood for pharmacokinetics (Visit 6 only) MUST be drawn after efficacy and safety assessments are completed. Subjects should be instructed to record accurate dosing history (date/time) on their dosing card for the day prior to and day of their study visit.

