**Blood and urine samples MUST be drawn after efficacy and safety assessments are completed.**

#### **6.1.5 Early Termination**

Every effort should be made to have subjects who withdraw early from the trial return to the site to complete an Early Termination Visit and return any unused study drug.

The following activities should be performed:

- Blood pressure and pulse (in triplicate via automated machine)
- Body weight
- Physical examination
- Resting 12-lead ECG
- Laboratory tests
  - Serum chemistry panel
  - Hematology
  - Urinalysis
  - Urine pregnancy test for females of child-bearing potential
- AISRS
- BRIEF-A
- DERS
- ASQ
- CGI-S
- CGI-I
- Follow-up C-SSRS
- AE assessment
- Concomitant medications assessment
- eCRF entry for early withdrawal
- Study drug accountability

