#### **6.4.3 Electrocardiography**

A 12-lead ECG will be recorded at Screening (Visit 1), End of Study (Visit 7) and at an Early Termination Visit (if necessary) by the Investigator or other designated, qualified individual from the study site. The ECGs will be assessed by a central reader(s). ECGs can be performed at unscheduled visits, per the Investigator's discretion.

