8.7 Vital Signs

Blood pressure and pulse will be assessed at all study visits and will be taken using automated machines programmed to take 3 consecutive readings (at least 2 minutes apart). Respiratory rate, height for BMI, and temperature will be measured at Screening (Visit 1) only.

Systolic blood pressure, diastolic blood pressure, pulse, respiratory rate, and temperature will be summarized descriptively for each visit, including change from Baseline (where applicable).

In addition, the incidence of sponsor defined potentially clinically significant (PCS) post-treatment vital sign values will be presented by treatment group and visit to examine the frequency and percentage of subjects that meet the PCS criteria outlined below:

- Heart Rate
 - ≥ 20 bpm increase
 - ≥ 20 bpm decrease
- Systolic Blood Pressure
 - ≥ 20 mmHg increase
 - ≥ 20 mmHg decrease
- Diastolic Blood Pressure

- ≥15 mmHg increase
- ≥15 mmHg decrease
- Weight
 - ≥5% increase
 - ≥5% decrease

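### Vital signs at Visits 6 and 7 can be a mix of pre-dose and post-dose readings that SAP 8.7 tabulates together, which would be expected to dilute the full-dose effect by an amount the documents do not allow to be calculated

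*Protocol*

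**What the plan says.** Protocol 6.4.2 states: "Blood pressure and pulse will be assessed at all study visits and will be taken using automated machines". It adds three readings, a minimum gap between them and a seated rest, but no time relative to the dose. Protocol 6.4.3 states: "A 12-lead ECG will be recorded at Screening (Visit 1), End of Study (Visit 7) and at an Early Termination Visit", again with no dose-relative time. The Schedule of Events (Table 6.1.1) and the visit lists in 6.1.3 to 6.1.5 supply none either.

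On PK sampling, Protocol 6.2.3.3 says: "The samples collected will include pre-dose up to approximately 6 hours following drug administration on planned subject visit days (Visit 6 and Visit 7"). SAP 9 repeats this. On the order of procedures, Protocol 6.1.3 says of the Visit 6 PK blood that it "MUST be drawn after efficacy and safety assessments are completed". The line that closes the Visit 7 list in 6.1.4 says: "Blood and urine samples MUST be drawn after efficacy and safety assessments are completed".

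SAP 8.7 says that blood pressure and pulse "will be summarized descriptively for each visit, including change from Baseline", and presents potentially clinically significant (PCS) changes by treatment group and visit. A pulse rise of 20 bpm or more is one PCS criterion. Protocol 6.1.3 and 6.2.3.3 have subjects record dose times on a dosing card for the day before and the day of the PK visits. No planned safety analysis uses them.

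**The concern.** Protocol 3.2.2 lists vital sign changes and ECG changes among the safety measures. Protocol 1.1.2 describes the drug as a sympathomimetic with cardiovascular activity. A reading taken many hours after the last dose is likely to show less of that activity than one taken a few hours after a dose. If the two kinds of reading share one row of a table, the mean change and the PCS rate on active drug move toward placebo by an amount that depends on clinic scheduling.

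Two features make this matter more. The possible mixing falls at the only scheduled visits on 40 mg/day. Also, no PK sample is planned at Visits 3 to 5, so the share of pre-dose readings may differ between those visits and Visits 6 and 7. A trend across visits in the 40 mg arm is then not a clean dose trend.

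**Working it through.** The plan gives no time-since-dose figure, so there is none to reproduce.

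**What follows from the text**

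1. *Order.* Blood follows the safety assessments at Visits 6 and 7. If the PK sample is pre-dose, the vital signs before it are pre-dose too. At Visit 7 so is the ECG; none is scheduled at Visit 6.
2. *Interval.* Protocol 1.3 puts the first dose on awakening and the second 4 to 6 hours later. From the second dose to the next morning's dose time is 24 − 6 = 18 hours to 24 − 4 = 20 hours, with a stable waking time. A 2-hour shift in waking either way gives 16 to 22 hours. If pre-dose means before the *second* dose, the reading is only 4 to 6 hours after the first.
3. *Visits affected.* In Protocol Table 5.3.2 the kit assigned at Visit 4 gives 20 + 10 = 30 mg/day and the kit assigned at Visit 5 gives 20 + 20 = 40 mg/day. Readings on 40 mg/day are therefore scheduled only at Visits 6 and 7.

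**Illustrative size (assumed inputs, not document figures)**

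Assume one compartment, an absorption half-life of 0.75 h, two equal doses at 0 and 5 h, steady state, and effect proportional to concentration. Let r be the pre-dose effect divided by the average effect from 0.75 to 10 h after the first dose. That interval is only an averaging choice in the model.

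| Elimination half-life (assumed) | r |
|---|---|
| 8 h | 0.32 |
| 10 h | 0.41 |
| 12 h | 0.48 |
| 14 h | 0.54 |

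Understatement of the mean change = f × (1 − r), where f is the share of readings that are pre-dose.

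- f = 25%: 0.25 × 0.46 = 11.5% to 0.25 × 0.68 = 17%.
- f = 10% to 50%: 0.10 × 0.46 = 4.6% to 0.50 × 0.68 = 34%.

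A cruder version uses the level just after the last dose as the reference, so that r = 2^(−t/half-life) with t = 18 to 20 h. For the same half-lives and f = 25% it gives about 15% to 21%. The figure depends on the model.

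*PCS rate for a pulse rise of 20 bpm or more.* Assume a true post-dose mean rise of 6 bpm with SD 9 or 11, and r rounded to 0.3 to 0.5. The normal tail area above 20 bpm, and the pooled rate 0.75 × post-dose + 0.25 × pre-dose, are:

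| SD | All post-dose | All pre-dose | Pooled at f = 25% |
|---|---|---|---|
| 9 | 6.0% | 2.2% to 2.9% | 0.75 × 6.0 + 0.25 × 2.2 (or 2.9) = about 5.0% to 5.2% |
| 11 | 10.2% | 4.9% to 6.1% | 0.75 × 10.2 + 0.25 × 4.9 (or 6.1) = about 8.9% to 9.2% |

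The pooled rate falls by about one percentage point, or roughly one subject in an arm of 104. At f = 50% the fall is about two to three subjects.

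**The case against.** The strongest reply is that pre-dose attendance may be uncommon. No section tells subjects to hold a dose. Dosing on awakening runs through Day 36, so the ordinary visit is post-dose. The PK sentence gives a range of sample times, not a visit instruction, and with two doses a day it may mean before the second dose. The collection instructions sit in a laboratory manual that is not among the documents. This stands as a limit on size: the pre-dose share is unknown. It does not remove the point, because the plan names pre-dose samples and its own order of procedures makes the vital signs pre-dose whenever such a sample is taken.

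It is also true that the safety analyses are descriptive, so no test is affected. Randomization should make the timing mix similar across arms. But balance does not prevent dilution: placebo has no drug effect to lose, so the difference from placebo shrinks.

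Protocol 6.4 speaks of AE assessment at post-dose visits. In context this means visits after study drug has started, and it does not set the timing of vital signs.

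A reader might go further in three ways that the documents do not support:

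- *That Visit 3 readings fall 24 hours after the last active capsule.* The Week 1 second dose is placebo, but no PK sample or pre-dose attendance is planned at Visit 3.
- *That readings fall outside a known effect window.* Protocol 1.1.3 says that the marketed product "demonstrated efficacy beginning at 45 minutes and continuing through 10 hours after administration of a single dose". This is efficacy in children aged 6 to 12. It is not a cardiovascular window in adults on repeated doses, and it does not say that the effect ends at 10 hours.
- *That the SAP pools on-treatment ECGs.* SAP 8.8 summarizes only Screening ECGs and lists the rest. The planned ECG change summary is in Protocol 9.8.3.

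**Conclusion.** The point holds for vital signs at Visits 6 and 7. The timing is left open, pre-dose PK samples are planned, the order of procedures ties the safety readings to them, and SAP 8.7 tabulates by visit without regard to time since dose. For the ECG, the point is limited to an unrecorded timing at Visit 7 and to any change summary made under Protocol 9.8.3.

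The direction, toward placebo, is an inference from the drug's acknowledged cardiovascular activity. The size cannot be calculated from the documents. It rests on an assumed half-life, an effect proportional to concentration, an assumed pre-dose share and, for the PCS rate, an assumed pulse rise and SD. With 25% of readings pre-dose, the mean change is understated by about 11.5% to 17% and the PCS pulse rate falls by about one percentage point.

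A reader might infer that the PCS rate drops from 6–10% to 2–6%. That contrast sets all-post-dose against all-pre-dose readings, and the planned table would not show it. This is a modest weakness with a cheap remedy.

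**What to change.** - *SAP 8.7:* for Visits 6 and 7, use the dose times on the dosing card to present change from Baseline and PCS rates separately for pre-dose and post-dose readings, or by time since last dose. Keep the by-visit table beside them.
- *SAP 8.8:* show time since last dose in the Visit 7 ECG listing, and in any ECG change summary made under Protocol 9.8.3.
- *Check that the data allow it:* the documents do not say whether the clock time of the vital-sign reading is captured. If it is not, a time field is needed. State also whether pre-dose in Protocol 6.2.3.3 refers to the first or the second dose.
- *Optional:* record the last dose time at Visits 3 to 5 too, so that the trend over visits can be read.

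The cost is one extra table and smaller groups. At a 25% share, the pre-dose group would be about 0.25 × 104 = 26 per arm before dropout. No change to the order of measurement is needed. If one were wanted, the blood-last rule in Protocol 6.1.3 and 6.1.4 would have to be amended as well, since drawing the PK sample first would contradict it.

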#### **6.4.3 Electrocardiography**

A 12-lead ECG will be recorded at Screening (Visit 1), End of Study (Visit 7) and at an Early Termination Visit (if necessary) by the Investigator or other designated, qualified individual from the study site. The ECGs will be assessed by a central reader(s). ECGs can be performed at unscheduled visits, per the Investigator's discretion.

#### **6.4.4 Hematology, Serum Chemistry and Urinalysis**

At Screening (Visit 1), End of Study (Visit 7) and at an Early Termination Visit (if necessary), laboratory tests will include a non-fasting serum chemistry panel, hematology (complete blood count), and urinalysis. Laboratory assessments are optional at Unscheduled Visits. For a complete list of laboratory tests, please see [Appendix A](#).

CYP 2D6 genetic testing will be performed only at Baseline (Visit 2) for those randomized subjects who opt in. Subjects who opt out are still eligible for the study. **During the trial, CYP 2D6 testing results will be blinded to the subject and investigative site in order to ensure protocol efficacy and safety assessments remain unbiased.**

Detailed sample collection, handling, processing, and shipment instructions will be provided by Sponsor's laboratory designee prior to the start of the study.

#### **6.4.5 Pregnancy Test and Contraceptives for Females of Child-Bearing Potential**

At the Screening Visit (Visit 1), a serum pregnancy test will be performed for all female subjects of child-bearing potential.

Urine dipstick pregnancy tests will be performed onsite at Visit 2 (Baseline) and Visits 4, 6, and 7 (End of Study) or early termination visit (if necessary) and may be performed at any time during study participation, if pregnancy is suspected. If positive, confirmation should be performed via a serum pregnancy test.

Moreover, females of child bearing potential must agree to use adequate birth control methods to prevent pregnancy throughout the study. Examples of medically highly effective forms of birth control include:

- Surgical sterility (via vasectomy, hysterectomy, or bilateral ligation) or post-menopausal females
- Sexual partner is sterile, or of the same sex
- Implants of levonorgestrel in females
- Oral contraceptive (combined or progesterone only) in females
- Double-barrier method (any combination of physical and chemical methods)
- Intrauterine device in females, or other method with published data showing that the lowest expected failure rate is less than 1% per year
- Complete abstinence from penile-vaginal intercourse

#### **6.4.6 Drugs of Abuse Testing**

A urine test for drugs of abuse will be performed at the site during Visit 1 (Screening) and Visit 2 (Baseline). The following drugs will be included: amphetamine, barbituates, benzodiazepines, cocaine, opiates, methadone, methamphetamine, and phencyclidine (PCP).

